# The date of BAPE diagnosis will be recorded. This is defined as the date on the pathology report describing features of BAPE that meet they eligibility criteria as explained in section 6.

Imaging, pleural fluid and blood results should be recorded at first presentation.

Cases can be entered throughout the period that the study is open. This includes cases diagnosed with BAPE with less than 2 years follow-up at the point the study opens, so long as 2 years follow-up has concluded by the time they are enrolled.

Demographics	Age*, Gender
Asbestos Exposure History	Occupational or environmental Nature of Occupation
CT Findings*	
 
Benign or Malignant Features
 
Based on previously reported criteria (5,11)
 
Calcified Pleural plaques
 
Present or Not Present
 

CXR appearance*	Effusion Laterality Effusion Size: • Small effusion (<50% thorax) • Large effusion (≥50% thorax)
Blood Tests*	Haemoglobin Neutrophils Lymphocytes Platelets CRP Albumin LDH Total Protein

Pleural Fluid	Total protein Albumin LDH Glucose Colour Cytology
LAT/VATS Findings	Date index procedure performed Were adequate views obtained? Which surfaces were abnormal? What was the nature of the abnormality/ies? • Smooth • Macro-nodular • Micro-nodular Number of biopsies Did the lung prove non-expansile (based on BTS criteria (≥50% re-apposition) (20) Did the subject have pleurodesis? Did the subject have an IPC placed? Histology, Cytology, Pleural Fluid Chemistry Results
Follow-up Data	Record any new pleural diagnosis since LAT/VATS Record whether MPM diagnoses within 2 years of index LAT/VATS date

\*at presentation

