### 4.5.2 Retrospective Cohort Study End-points

The **Primary End-Point** shall be the rate of MPM transition, defined as the number of eligible patients diagnosed with MPM within 2 years of the index diagnosis of BAPE divided by the total number of eligible patients.

The **Secondary End-Point** shall be a logistic regression model for MPM transition using baseline data as predictors.

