### 6.4 Retrospective Cohort Study Case Identification

Electronic databases will be used to identify cases meeting the study eligibility criteria. Existing databases in the trial centres involved contain data on approx. 1000 patients that have undergone LAT. These database should contain approx. 300 cases of BAPE based on previously published BAPE incidence of 30% in this population (2). Existing databases from VATS and image guided biopsy cases will also be used.

Cases can be entered throughout the period that the study is open. This includes cases diagnosed with BAPE with less than 2 years follow-up at the point the study opens, so long as 2 years follow-up has concluded by the time they are enrolled. The retrospective study will end after 12 months from opening and therefore patients who had a diagnosis of BAPE following LAT on or before 31/11/17 could be recruited.

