# 8 Retrospective Study Data Collection and Recording

The following data will be recorded retrospectively for all eligible patients using LAT/VAT/image guided biopsy databases and electronic health records at the study centres. A data collection form (.x/s) will be provided, including pre-populated study IDs. All data will be recorded in a linked anonymised format.

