#### **10.2.2** Retrospective Cohort Study

Results will be reported using simple descriptive statistics. The **primary end-point** shall be the rate of MPM transition. This will be calculated by dividing the number of eligible patients diagnosed with MPM within 2 years of the index diagnosis of BAPE by the total number of eligible patients. The **secondary end-point** shall be based on the content of a logistic regression model for MPM transition generated using baseline data as candidate predictors.

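### The retrospective follow-up items time MPM from the LAT/VATS date, while the primary end-point times it from the BAPE pathology report, and image-guided biopsy cases may have no LAT/VATS date

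*Protocol*

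**What the plan says.** Protocol 4.5.2 defines the retrospective primary end-point as a proportion, counting those "diagnosed with MPM within 2 years of the index diagnosis of BAPE divided by the total number of eligible patients". Section 10.2.2 repeats the same origin: "diagnosed with MPM within 2 years of the index diagnosis of BAPE by the total number of eligible patients". Section 8 says that the date of BAPE diagnosis will be recorded and fixes what it is: "This is defined as the date on the pathology report describing features of BAPE". That definition is not limited to any biopsy route.

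The follow-up row of the data table in section 8 holds two items. One is "Record any new pleural diagnosis since LAT/VATS" and the other is "Record whether MPM diagnoses within 2 years of index LAT/VATS date". The only procedure date listed, "Date index procedure performed", stands in the LAT/VATS findings row. There is no matching row for image-guided biopsy.

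Image-guided cases are nevertheless in the cohort. Section 6.4 states "Existing databases from VATS and image guided biopsy cases will also be used", and section 8 draws on "LAT/VAT/image guided biopsy databases and electronic health records at the study centres". Section 6.1 makes histology mandatory for every retrospective case.

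**The concern.** The definition and the data items that feed it start the 2-year window at different points. A site that follows section 8 literally answers a question the end-point does not ask. For a patient biopsied only under image guidance, the question has no starting date. The site must then leave it blank, substitute a date of its own choosing, or use a later LAT.

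The last choice can matter. Section 5.1.3 says repeat biopsies are pursued when effusion recurs. A patient with a benign image-guided biopsy and a later LAT showing MPM is a transition on the pathology-report clock if the LAT falls within 2 years. On the LAT clock, MPM sits at day 0, and an item asking about diagnoses since LAT may miss it.

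The transition rate is this cohort's primary result and the input to the Meso-ORIGINS sample size. The synopsis and section 5.2 both warn that a rate below 12% could make that study unfeasible. An error that pushes the rate down would therefore bear directly on the decision.

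**Working it through.** **Inputs from the protocol.** Target 300 (10.1.2); about 1000 LAT database patients and 30% BAPE incidence (6.4, 10.1.2); 12% two-year transition rate (5.1.3); 850 patients for about 100 MPM cases in Meso-ORIGINS (synopsis).

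**Inputs assumed, because the protocol gives none.** The lag from procedure to pathology report; events spread evenly over 730 days; the image-guided share of the cohort; how a blank outcome item is handled.

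**Step 1: the plan's own figures.** 0.30 × 1000 = 300, as stated. 0.12 × 300 = 36 expected events. 850 × 0.12 = 102, against the stated 100. The number needed for 100 events at 12% is 100 / 0.12 = 833.

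**Step 2: sampling error for scale.** The Wilson 95% interval for 36/300 is about 8.8% to 16.2%, that is 3.2 points below and 4.2 points above 12%.

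**Step 3: LAT/VATS cases.** Here the two origins differ by the reporting lag d. Taking all 300 as LAT/VATS cases, events moved = 36 × d / 730 and the change in rate = 12 × d / 730 points.

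| Lag (days) | Events moved | Change (points) |
|---|---|---|
| 3 | 0.15 | 0.05 |
| 7 | 0.35 | 0.12 |
| 14 | 0.69 | 0.23 |
| 30 | 1.48 | 0.49 |

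**Step 4: image-guided cases.** If a share f of the cohort has the item blank and a blank is read as no MPM, the observed rate is 12% × (1 − f), and the number needed for 100 events is 100 / (0.12 × (1 − f)).

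| Share f | Observed rate | N for 100 events |
|---|---|---|
| 5% | 11.4% | 877 |
| 10% | 10.8% | 926 |
| 20% | 9.6% | 1042 |
| 30% | 8.4% | 1190 |

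At f = 30% the shift is 12.0 − 8.4 = 3.6 points, about the size of the sampling half-width but always in one direction. If blanks were dropped instead, and the rate did not differ by route, the rate would stay near 12% but precision would fall. At f = 30%, 210 patients remain, with about 25 events and an interval of about 8.2% to 17.0%.

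**Step 5: can it be repaired afterwards?** The listed items include the BAPE diagnosis date but no MPM diagnosis date. From those items alone, an analyst cannot re-time the outcome against the defined end-point.

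**The case against.** The best defence is that the end-point itself is sound. Sections 4.5.2 and 10.2.2 agree, section 8 dates the diagnosis, and the synopsis describes follow-up for MPM within two years without any LAT/VATS anchor. On that view, two table entries have simply not been updated to match the definition.

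Much of this stands, and it rules out several stronger readings:

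- A reader might infer that image-guided cases have no index date, or that the primary rate is undefined for them. They do have one. Histology is mandatory, so each has a pathology report, and that report is the end-point's own origin. What they may lack is the LAT/VATS date that the follow-up items ask for.
- A reader might infer that the lag alone could move several events. With even spread, moving 5 of 36 would take 5 × 730 / 36 ≈ 101 days. Nothing in the protocol suggests a lag of that length.
- A reader might assume that image-guided cases are a large part of the cohort. The protocol gives no share. It expects about 300 cases from LAT databases alone, so the share may be small.
- A reader might conclude that the outcome can never be re-derived. The spreadsheet itself is not shown, and the sites hold linked records that could be queried. The supportable statement is that the listed items name no MPM date.

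The defence does not remove the contradiction. The protocol fixes both origins and they differ, so this is not a detail left open for a statistical analysis plan.

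**Conclusion.** The point holds as a mismatch between a clearly defined end-point and the items that collect it. Followed literally, section 8 gathers the primary outcome from the wrong origin, and its outcome item cannot be answered for patients biopsied only under image guidance.

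For LAT/VATS cases the consequence is minor, at most about 0.5 points on the assumptions of Step 3 and well inside sampling error. The larger exposure is the image-guided group: 0.6 to 3.6 points downward for an assumed share of 5% to 30%, a true rate of 12%, and blanks counted as no MPM. These figures show a range under assumptions; they do not estimate what will happen. The contradiction itself rests on no assumption. It should be corrected before extraction, chiefly because the remedy is so cheap.

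**What to change.** In section 8, word both follow-up items from the date of BAPE diagnosis as that section already defines it, for LAT, VATS and image-guided cases alike. Section 8 does not say which report counts when a patient has several, so state that it is the first pathology report meeting section 6.1.

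Add the date of MPM diagnosis to the listed items. Derive 2-year status centrally from the two dates, so that it does not depend on each site's reading of the window.

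The cost is one added date field, drawn from health records the sites already consult, and two reworded items. The end-point definition and the target of 300 are unchanged.

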# 9 Patient Withdrawal

Patients will be withdrawn from the study if any of the following occur:

- Patient withdrawal of consent
- Clinical opinion of the doctor that the patient should no longer continue in the study

Patients can withdraw their consent for ongoing participation in the study at any point. If this occurs:

- Withdrawal of consent will be clearly documented, along with the level of consent withdrawal and the reason (if the patient has given any)
- A consent withdrawal notification form will be completed.

# **10** Statistical Considerations

10.1 Sample Size

#### **10.1.1 Prospective Feasibility Study**

Each centre performs 30-50 LATs/year (total 120-200/year). Based on a historical incidence of BAPE in 30% in LAT cases (2) we expect there will be 40-60 patients available. The estimated sample size is 54 patients over 12 months, in whom we predict the study will be feasible in a maximum of 50% (n=27).

#### **10.1.2** Retrospective Cohort Study

The target sample size is 300. Existing databases in Glasgow, Bristol, Manchester & Oxford contain data on approx. 1000 patients. Based on a 'BAPE' incidence of 30% (2) in LAT cases, this should be feasible and would be more than double the size of the previous study (2) on which the Meso-ORIGINS sample size estimate is based.

### 10.2 Statistical Analysis Plan

#### **10.2.1 Prospective Feasibility Study**

Results will be reported using simple descriptive statistics. The **Primary Endpoint** shall be met if repeat LAT for research purposes is acceptable to the patient at Visit 2 *and* LAT is technically feasible at Visit 2.

#### **10.2.2** Retrospective Cohort Study

Results will be reported using simple descriptive statistics. The **primary end-point** shall be the rate of MPM transition. This will be calculated by dividing the number of eligible patients diagnosed with MPM within 2 years of the index diagnosis of BAPE by the total number of eligible patients. The **secondary end-point** shall be based on the content of a logistic regression model for MPM transition generated using baseline data as candidate predictors.

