# 2 Synopsis

Study Title	The Meso-ORIGINS Feasibility Study
Study Design	Multi-centre prospective feasibility study incorporating a retrospective multi-centre cohort study
Study Participants	Patients with Benign Asbestos Pleural Effusion (BAPE)
Sample Size	Prospective observational study: n = 54 (or n=27 feasible patients, whichever is reached first). Retrospective cohort study: n=300
Study Period	12 months
Sponsor	NHS Greater Glasgow & Clyde
Background and Rationale	MPM typically develops 30-50 years after inhalation of asbestos and is often presaged by radiological +/- clinical evidence of chronic pleural inflammation, and frequently by overt pleural effusion. The base agnostic pattern of DNA damage recently reported in MPM also suggests a prominent role for immune or inflammatory triggers. However, the recent genomic characterisation of MPM (1) poses major questions regarding the pressures that drive MPM evolution, being dominated by loss of tumour suppressors, with few protein-altering mutations in known oncogenes (1). Greater understanding of the driving (oncogenic) +/- permissive (immunological) events is required to design effective MPM treatments.
	In a future study called Meso-ORIGINS, we aim to define in vivo the key biological events that drive or permit evolution of MPM. Meso-ORIGINS will involve serial biological surveillance (using circulating markers, imaging +/- repeat pleural fluid and biopsies) over a 2-year period preceding the diagnosis of MPM. This will be achieved by recruitment of 850 patients with BAPE, of whom an estimated 12% (n=100) will develop MPM based on previous data (2). This will facilitate unprecedented surveillance of the key early biological events in MPM tumourigenesis.
	
 
The current feasibility study will address important areas of uncertainty regarding the current Meso-ORIGINS design, including:
 
within a prospective feasibility study, the technical feasibility and patient acceptability of a surveillance protocol including LAT, and alternative strategies limited to blood tests, imaging +/- pleural fluid sampling
 
within a retrospective cohort study, greater precision regarding the sample size estimate (currently n=850). This is based on a single study that reported a 2-year MPM transition rate of 12% (95%CI 4.5% - 26.4%) (2). If the true rate is close to the lower end of this 95% CI this may mandate an unfeasible sample size.
 

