## 4.5 Retrospective Cohort Study Objectives and End-points

#### 4.5.1 Retrospective Cohort Study Objectives

The primary objective is to determine more precisely the rate of transition to MPM in patients diagnosed with BAPE.

The secondary objective is to identify baseline predictors of transition to MPM, allowing refinement of the current Meso-ORIGINS eligibility criteria

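### The logistic model of MPM transition has an open candidate list of about 22 to 31 parameters against about 36 expected events, so an ordinary or stepwise fit would be an unreliable basis for refining Meso-ORIGINS eligibility

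*Protocol*

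**What the plan says.** Section 10.2.2, which sits under the protocol's own statistical analysis plan heading (10.2), bases the secondary end-point of the retrospective cohort on the content of "a logistic regression model for MPM transition generated using baseline data as candidate predictors". Section 4.5.1 gives the purpose: to "identify baseline predictors of transition to MPM, allowing refinement of the current Meso-ORIGINS eligibility criteria".

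Section 8 lists what is recorded: demographics, asbestos exposure, CT and chest X-ray findings, blood tests, pleural fluid results and LAT/VATS findings. Neither section shortlists predictors or limits their number.

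On size, section 10.1.2 states: "The target sample size is 300". That figure comes from the number of cases available, and it is defended only by comparison with the earlier study behind the transition-rate estimate. Nothing in the protocol sizes the regression model.

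**The concern.** The end-point is what the model contains, so the choice of predictors is itself the result. When the candidates are nearly as numerous as the events, ordinary maximum likelihood or stepwise selection picks up chance associations, exaggerates coefficients and reports discrimination that does not carry over to new patients.

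The stated use makes this matter. If entry to a study planned at 850 patients were refined on such a model, the refinement could rest largely on noise.

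**Working it through.** **Inputs from the protocol**
- Database size and BAPE share (10.1.2): "Existing databases in Glasgow, Bristol, Manchester & Oxford contain data on approx. 1000 patients" and "Based on a 'BAPE' incidence of 30% (2) in LAT cases".
- Two-year MPM transition rate (Synopsis and 5.1.3): 12%, 95% CI 4.5% to 26.4%.
- Recorded variables: the table in section 8.

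**Assumed, not in the protocol:** Nagelkerke R² of 0.15, 0.30 or 0.50.

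**1. The plan's own figure.** 1000 × 0.30 = 300. The target reproduces as a count of available cases.

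**2. Expected events = N × rate.**
- 12%: 300 × 0.12 = 36
- 4.5%: 300 × 0.045 = 13.5
- 26.4%: 300 × 0.264 = 79.2

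**3. Candidate parameters**, at one per binary or continuous item:

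| Group | Parameters |
|---|---|
| Age, gender | 2 |
| Asbestos exposure | 2 |
| CT | 2 |
| Chest X-ray | 2 |
| Blood tests | 8 |
| Pleural fluid | 6 |
| LAT/VATS (views 1, surfaces 1, nature of abnormality 2, number of biopsies 1, non-expansile lung 1, pleurodesis 1, IPC 1, histology 1) | 9 |
| **Total** | **31** |

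Without LAT/VATS items: 31 − 9 = 22. Coding occupation, surfaces, fluid colour or histology in several categories would add more.

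**4. Events per parameter = events / parameters.**

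| Rate | 31 parameters | 22 parameters |
|---|---|---|
| 4.5% | 13.5/31 = 0.44 | 13.5/22 = 0.61 |
| 12% | 36/31 = 1.16 | 36/22 = 1.64 |
| 26.4% | 79.2/31 = 2.55 | 79.2/22 = 3.60 |

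**5. Expected shrinkage S.** Solve n = P / [(S − 1) ln(1 − R²cs/S)] at n = 300. At a 12% rate the maximum Cox-Snell R² is 1 − exp{2[0.12 ln 0.12 + 0.88 ln 0.88]} = 0.52, so R²cs = 0.52 × Nagelkerke R².

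| Nagelkerke R² | R²cs | S, P = 31 | S, P = 22 | S, P = 4 | P giving S = 0.9 |
|---|---|---|---|---|---|
| 0.15 | 0.078 | 0.45 | 0.54 | 0.86 | 2.7 |
| 0.30 | 0.156 | 0.63 | 0.71 | 0.93 | 5.7 |
| 0.50 | 0.260 | 0.76 | 0.81 | 0.96 | 10.2 |

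The usual target is S of at least 0.9. At a 26.4% rate, 31 parameters still give only 0.53, 0.70 and 0.81. For 31 parameters to reach 0.9 at a 12% rate, n would have to be about 3420, 1629 or 910 across the three R² values.

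**6. Simulation.** Unpenalised logistic models, n = 300, 12% event rate, independent normal predictors all entered, 200 data sets each; medians shown.

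| Setting | True c | Apparent c | c in new data | Calibration slope |
|---|---|---|---|---|
| 31 predictors, none real | 0.50 | 0.78 | 0.50 | 0.00 |
| 31 predictors, 5 real | 0.75 | 0.85 | 0.67 | 0.34 |
| 3 predictors, all real | 0.71 | 0.72 | 0.70 | 0.88 |

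**7. What 36 events can carry.** Ten events per parameter gives 36/10 = 3.6. The shrinkage criterion gives 2.7 to 5.7 for R² of 0.15 to 0.30. Together these suggest about 3 to 5 parameters.

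**The case against.** **The protocol does not say that every recorded item enters the model.** True. The count of 31 is read from the data collection table, which also serves descriptive reporting. A reader might infer that the whole table is to be fitted, but the text does not say so. It does leave the set open, and over-fitting depends on the candidates offered as well as on those kept. Leaving out all LAT/VATS items does not change the conclusion.

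**Shortlists, penalisation and validation commonly belong in a later analysis plan.** This has force. A separate plan could cure most of the problem, so it would be wrong to conclude that the model will inevitably be over-fitted; that holds for unpenalised or stepwise fitting. A later plan cannot, however, raise the number of events, which follows from the target of 300 and the transition rate. The protocol itself pairs that target with an open candidate set and a consequential use.

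**The magnitudes rest on assumptions.** They do: R² is not in the documents, and the simulation uses independent normal predictors all forced in, although many recorded items are binary. This is why ranges are shown. No combination examined brings 22 or 31 parameters to the 0.9 target.

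**Pleurodesis and IPC.** Because section 8 asks "Did the subject have pleurodesis" and also whether an IPC was placed, a reader might infer that the list contains treatments that could not be known at screening and must be dropped. The protocol does not support this. Prospective patients are approached after the BAPE diagnosis (7.2), and both items are on the Visit 1 Baseline CRF for patients who had LAT (7.4.1).

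**The consequence is indirect.** Section 4.5.1 speaks only of "allowing refinement of the current Meso-ORIGINS eligibility criteria". No rule converts model output into an eligibility change, so harm would need a further decision. That limits the severity.

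**Conclusion.** The concern holds in conditional form. On the protocol's own figures, about 36 events (about 14 to 79 over the CI) face about 22 to 31 candidate parameters. That is 1.2 to 1.6 events per parameter at 12%, and 2.6 to 3.6 at the upper limit. An ordinary or stepwise logistic model built from these candidates would give unreliable selection and inflated discrimination: shrinkage of about 0.45 to 0.76 with 31 parameters, and an apparent c-statistic of about 0.78 from noise alone.

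This rests on minimum coding of the section 8 items, the full 300 patients with usable data, the quoted transition rate, and an assumed Nagelkerke R² of 0.15 to 0.50. Missing retrospective data would worsen the ratio. It is a point the sponsor should address for a secondary end-point. It does not affect the primary transition-rate estimate.

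**What to change.** In section 10.2.2, state that:
- the model will use a small set of predictors named before data extraction, about 3 to 5 parameters at 36 events, revisited if the event count differs;
- it will be fitted with penalisation (ridge or Firth);
- the c-statistic and calibration slope will be reported after bootstrap correction for optimism;
- the remaining section 8 variables will be reported descriptively only;
- any refinement of Meso-ORIGINS eligibility will rest on the optimism-corrected results.

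The range of 3 to 5 is a judgement that depends on R². At R² = 0.15, four parameters give shrinkage of 0.86, just short of 0.9, so penalisation and optimism correction are still needed with a short list.

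Pleurodesis and IPC need not be removed on grounds of availability.

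Cost: a few sentences and a few hours of analysis, with no new data. The downside is that fewer predictors are explored in the model.
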